7.4 Test Article(s) (Study Drug(s) and/or Study Device(s))

7.4. 1 Description

Pioglitazone hydrochloride 45mg tablets will be overencapsulated to match placebo capsules for this study.

Pioglitazone, a peroxisome proliferator-activated (PPAR γ) receptor agonist, is FDA-approved as an anti-glycemic agent for the treatment of type-2 diabetes that has shown promise for secondary stroke prevention in clinical stroke trials [3-5], but has thus far not been studied as an acute intervention for acute diabetic stroke. PGZ acts primarily by decreasing insulin resistance.

7.4. 2 Treatment Regimen

Following oral administration, PGZ is first measurable in serum within 30 minutes, with peak concentrations observed within 2 hours. It is relatively insoluble but can be crushed and given through a feeding tube. Serum concentrations of total PGZ (PGZ plus active metabolites) remain elevated 24 hours after a once daily dosing.

The treatment group will receive 45 mg of PGZ orally within 18 hours of stroke symptom onset or last known well and subsequently at 24h and 48h after the initial dose. This represents the highest recommend dose in humans and is selected to achieve the highest blood concentration of PGZ as quickly as possible following the stroke event. The control group will receive placebo orally at the same time points. Both groups will be treated identically and receive best standard of care.

Some acute ischemic stroke patients experience trouble swallowing (dysphagia), and all stroke patients are therefore routinely assessed for dysphagia as part of their routine clinical care. If patients are not able swallow, PGZ/placebo will be crushed and administered via a feeding tube.

To avoid unblinding of the study team if the capsules have to be opened/crushed for administration, a warning label will be placed on study drug package telling the bedside nurse not to reveal the contents of the capsule to study team members. Study team members will not administer drug to any patients who are unable to swallow.

There is no provision to provide study treatment after the study.

7.4. 3 Method for Assigning Subject to Treatment Groups

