Precautions: PGZ is metabolized in the liver. Therefore, any drug which is a strong CYP2C8 inhibitor or inducer may affect the efficacy of PGZ. Subjects who require these medications during study drug treatment are permitted into the study with additional monitoring/precautions in place:

1. Strong CYP2C8 inhibitors (such as gemfibrozil) increase PGZ concentrations. Therefore, gemfibrozil will be held for the 3 day duration of the study treatment and started after 24 hours of the last dose of study drug.
2. CYP2C8 inducers (e.g., rifampin) may decrease PGZ concentrations. Therefore, these medications will be spaced 4 hours after administration of the study drug.

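### The 4-hour gap for CYP2C8 inducers does not address an interaction that the protocol attributes to liver metabolism, and the hold for strong CYP2C8 inhibitors names gemfibrozil only

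*Combined protocol and SAP*

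**What the plan says.** The precautions in section 7.4.6.5 start from a metabolic mechanism: "PGZ is metabolized in the liver. Therefore, any drug which is a strong CYP2C8 inhibitor or inducer may affect the efficacy of PGZ". Patients on such drugs are not turned away: "Subjects who require these medications during study drug treatment are permitted into the study with additional monitoring/precautions in place". Two numbered items then give the specific measures.

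- Item 1, inhibitors. The risk is described for a class: "Strong CYP2C8 inhibitors (such as gemfibrozil) increase PGZ concentrations". The action names one drug: "gemfibrozil will be held for the 3 day duration of the study treatment and started after 24 hours of the last dose of study drug".
- Item 2, inducers. The item says that CYP2C8 inducers may lower PGZ concentrations, gives rifampin as an example, and sets one measure: "Therefore, these medications will be spaced 4 hours after administration of the study drug". There is no hold, and section 3.2 does not exclude inducers as such.

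Section 7.4.2 gives the kinetics that bear on the gap. On uptake: "PGZ is first measurable in serum within 30 minutes, with peak concentrations observed within 2 hours". On persistence: "Serum concentrations of total PGZ (PGZ plus active metabolites) remain elevated 24 hours after a once daily dosing". Doses are given at 0, 24 and 48 hours.

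**The concern.** A time gap is a remedy for two drugs that interfere with each other at intake. Section 7.4.6.5 describes something else, a change in how the liver clears PGZ, and no section names an absorption problem. The rule for inducers therefore does not do the job its own rationale sets. A patient already on an inducer can be enrolled under a precaution that is not shown to prevent lower PGZ exposure.

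The inhibitor item has a different gap. A patient on a strong inhibitor other than gemfibrozil can be enrolled with no specific measure, at a dose that section 7.4.2 describes as the top of the recommended range. Section 10.0 lists hypoglycemia and heart failure among the risks.

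At stake is altered exposure in a few PGZ patients: lower with an inducer, higher with an unheld inhibitor. In a pilot meant to inform the power analysis of a later trial (section 8.2), under-exposed patients would pull the observed effect toward zero.

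**Working it through.** The protocol states no figure on this point, so there is none to reproduce. The check is a timeline, a comparison of the two items, and an upper bound.

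**Timeline.** Inputs: doses at 0, 24 and 48 h, peak within 2 h, and drug plus active metabolites elevated at 24 h (all section 7.4.2); gap of 4 h (section 7.4.6.5). Assume an inducer taken once daily.

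- Inducer intake falls at 4, 28 and 52 h.
- Distance from the peak: 4 − 2 = at least 2 h after it. The gap clears intake and peak.
- Time from inducer intake to the next study dose: 24 − 4 = 20 h, or 20/24 = 83% of the dosing interval. Over that time the inducer has been taken and, on the protocol's statement, total PGZ is still elevated.
- Doses 2 and 3 each follow an inducer intake by 20 h.
- The rule says nothing about inducer taken before the first dose.

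The 83% counts hours. It does not estimate lost exposure.

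**The two items side by side.** Both rest on the same sentence about liver metabolism.

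| | Inhibitors (item 1) | Inducers (item 2) |
|---|---|---|
| Risk described for | strong inhibitors as a class | inducers as a class |
| Measure applies to | gemfibrozil only | the class |
| Measure | hold until 48 + 24 = 72 h after first dose | 4 h gap |

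A hold through treatment fits a metabolic interaction; a 4 h gap does not. In item 1 the measure is narrower than the risk.

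**Upper bound on dilution.** If one PGZ patient has no drug effect left, the arm's mean effect shrinks by 1/n.

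- n = 25 per arm (section 8.2): 1/25 = 4.0%.
- n = 22 per group for the intention-to-treat analysis (section 8.2): 1/22 = 4.5%.

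**How many patients.** The documents give no co-medication frequency. Assume, for illustration, that 0.5% to 4% of candidates take a strong CYP2C8 inducer or inhibitor.

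- Both arms, both drug types: 50 × 0.005 = 0.25 to 50 × 0.04 = 2.
- PGZ arm under 1:1 allocation: 0.25/2 = 0.125 to 2/2 = 1.
- If all of these were inducer users with no effect left: 0.125/25 = 0.5% to 1/25 = 4.0% expected dilution.

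Inhibitor users are exposed in the other direction and do not belong in that sum, so under this assumption the dilution would be smaller.

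**The case against.** Several points on the other side have weight.

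**The gap falls after the peak.** Section 7.4.2 says of the 45 mg dose: "This represents the highest recommend dose in humans and is selected to achieve the highest blood concentration of PGZ as quickly as possible". A reader might infer that the spacing rule defeats this aim. The documents do not support that. An inducer given at least 2 hours after the peak is compatible with a high early concentration, and nothing is said about how fast induction starts or how long it lasts.

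**The 24-hour statement covers metabolites too.** It does not show how much parent drug remains. That limits what can be said about its size. It does not rescue the rule, because the metabolites are described as active and the stated mechanism is still clearance by the liver.

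**Gemfibrozil may be shorthand for the class.** It is the only inhibitor named, and it is held. That reading is possible, but the sentence ordering the hold does not say so, and ward staff should not have to guess.

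**Rifampin.** A reader might infer that item 2 describes a patient who cannot enter, since exclusion 2 bars current antibiotic use. The documents do not classify rifampin, and section 7.4.6.5 covers drugs given from enrolment to the end of treatment, so the example can apply to a drug started after entry.

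**General safeguards exist.** Co-medications are monitored daily (7.4.6.5), glucose is checked at 2 hours and regularly afterwards, liver tests are confirmed before dose 3 (7.2), heart failure is watched for (10.0), and stopping rules apply (18.7). These can detect harm from over-exposure, but none corrects exposure. No PGZ level is among the tests listed in 7.1 and 7.2, so under-exposure would not be seen directly.

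**A lighter remedy is possible.** The sponsor could justify the 4-hour rule and simply record inducer users. Recording is already required, but it leaves in place a measure that does not match its rationale.

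**Conclusion.** The point holds as a minor correction. The inducer rule does not address the mechanism the protocol gives, and the inhibitor hold is narrower than the class described. Both follow from the text of 7.4.6.5 and 7.4.2.

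The size is small: at most 4.0% (4.5% in the intention-to-treat group) of the mean effect for each PGZ patient who loses the whole drug effect, which is an extreme assumption. The number of such patients is unknown and probably very small. The documents name only one inducer and one strong inhibitor, and they give neither a frequency nor the size of the exposure change.

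A reader might multiply the per-patient figure across several patients. The documents give no count to support that, and the assumed frequency range pools both arms and two drug types with opposite effects. Nor is there ground to infer a biased comparison: the rules are the same in both arms of a randomized, blinded trial.

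**What to change.** Three wording changes.

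1. **Inducers at entry (3.2 and 7.4.6.5).** Replace the 4-hour spacing, and the permission to enrol inducer users, with an exclusion in 3.2 for current use of a CYP2C8 inducer of the kind item 2 covers. Item 2 is not limited to strong inducers, so the exclusion should not be either.
2. **Inducers newly needed after randomization (3.3).** State that the drug is recorded, is not by itself a reason for removal under 3.3.1, and that the patient keeps the day 90 assessment and stays in the intention-to-treat analysis. Without this, the new exclusion could trigger removal under 3.3.1, and the reasons for which 3.3.2 requires a day 90 assessment do not clearly include a co-medication. Other removal rules still apply, for example where the drug is given for a new infection.
3. **Inhibitors (7.4.6.5, item 1).** Apply the existing hold to any strong CYP2C8 inhibitor that the treating physician judges can safely be held. Do not enrol a patient whose strong inhibitor cannot be held.

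Cost: a few candidates may lose eligibility. Under the assumed 0.5% to 4% for strong drugs, that is 0.25 to 2 per 50, fewer where an inhibitor can be held; the broader inducer wording could add to this by a number the documents do not give. A patient on a held inhibitor goes about 72 hours without it, as gemfibrozil users already do. Keeping a patient who newly starts an inducer accepts a small dilution, within the per-patient bound above, in exchange for a complete 90-day outcome.

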8.0 Subject Numbers and Statistical Plan

8.1 Number of Subjects

This study will enroll 50 hyperglycemic acute ischemic stroke patients.

8.2 Sample size determination

This is an exploratory study to accumulate pilot data. The sample size of this proposed pilot study is a total of 50 hyperglycemic adult patients with acute IS, (n=25 per treatment arm, study drug and placebo, respectively). The data from this pilot study will help the power analysis for a future clinical trial of PGZ in hyperglycemic acute ischemic stroke.

Based on preliminary studies, we predict that about 30% (n=15/50) of patients with acute stroke symptoms will be diagnosed as “stroke mimics” after enrollment, having conditions such as a complicated migraine, seizure, metabolic disturbances that are not strokes. These individuals will continue study participation and will serve as controls. We also predict an attrition rate of 18% (n=5) at 3 months. Therefore we aim to include a total of 44 enrolled patients (n=22/group) for the intention-to-treat analysis.

9.0 Data and Safety Monitoring Plan

9.1 Periodic evaluation of data

To monitor safety throughout the course of the study, every effort will be made to remain alert to possible AEs/SAEs. If an AE/SAE occurs, the first concern should be for the safety of the subject. If necessary, appropriate medical intervention will be provided. At the signing of the written consent form, each subject or his/her legally authorized representative and/or main caregiver must be given the names and telephone numbers of study site staff for reporting AEs/SAEs and medical emergencies.

As recommended by NCATS, our study team has identified an independent safety monitor for our study. [name] (endocrinologist) has kindly agreed to serve in this role. She will review every adverse event during the study (as described in the next paragraph) based on severity and relationship to the study treatment. She will also review patient safety regularly after every 10th patient enrollment.

In this study, any AE/SAE experienced by the subject between the time of first dose of study treatment and 24 hours after the last dose will be recorded on the electronic case report form, regardless of the severity of the event or its relationship to study treatment. During study treatment and visit after 90 days, the research team will assess the subject for AEs and will record any new AEs/SAEs or updates to previously reported AEs on the electronic case report form.

The data will be reviewed by the study statistician in the Public Health Science department. If our trial allows us to reach our predetermined alpha with fewer patients than our predicted sample size, than periodic evaluation will allow us to avoid randomizing patients to a treatment that is potentially inferior. The data will be reviewed once, when 50% of patients have been enrolled in each arm.

9.2 Data that are reviewed

Data collected as primary outcomes and safety profile for the study will be reviewed. Neurological function determined by NIHSS, mRS, MOCA, BI and GOS, discharge disposition and rate of infection will be reviewed. Liver function tests will be reviewed.

9.3 Method of collection of safety information

Safety information will be collected in the research database throughout the study. The safety of the study drug will be evaluated by clinical assessments and laboratory tests (see section 7.2).

9.4 Frequency of data collection

The data of neurological function (NIHSS, BI, mRS, GOS and MOCA) will be collected before initiation of study drug, at discharge from hospital, and at 90 days during the follow-up visit. Inflammatory markers and all biomarkers will be collected at baseline and 24 hours after each dose of study drug for three consecutive days (see also table of study events, section 7.2).

9.5 Individuals reviewing the data

[name] (endocrinologist) will review the efficacy and safety of the PGZ intervention.

9.6 Frequency of review of cumulative data

Data will be reviewed periodically, i.e. after collecting data of 5 patients, and will be discussed with team members approximately every three months.

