Participants will be randomized to either PGZ or placebo using an equal allocation ratio (1:1). The randomization will be performed using a random number generator via the PLAN procedure within SAS software, version 9.4 (SAS Institute Inc., Cary, NC). Personnel in the Department of Public Health Sciences (PHS) will use the PLAN procedure within SAS software to generate a randomization list using variable-size, random permuted blocks to ensure that the number of participants in each arm is balanced after each set of B randomized participants, where B is the block size. Personnel in PHS will choose the block sizes without revealing it to any of the investigators or study personnel who will be collecting and reviewing outcomes data. The PHS generated randomization list will be provided to Investigational Drug Services (IDS) who will be implementing the randomization for this trial.

7.4. 4 Subject Compliance Monitoring

Nursing staff will chart administration of study drug into the patient's EMR and study personnel will monitor and document the completion of all study procedures.

7.4. 5 Blinding of the Test Article

The investigators, study staff, subjects, and caregivers will be blinded to the subject's treatment assignments for the duration of the trial. Investigational pharmacy will be placed the investigational product into a plain capsule to insure that the investigative team remains blinded (see Section 7.4.6.3). To avoid unblinding of the study team members, if the capsules have to be

opened/crushed for administration by nursing staff, a warning label will be placed on study drug package telling the bedside nurse not to reveal the contents of the capsule to any study team member. Study team members will not administer any study drug.

All blood samples will be coded to maintain masking prior to analysis. The laboratory staff will be unaware of the condition and the treatment of the participants for whom they will conduct the assays as the samples will be identified only with a study number.

The results of the laboratory measurements will not be shared with the treating physicians, and will not impact patient care.

7.4. 6 Receiving, Storage, Dispensing and Return

7.4 .6.1 Receipt of Test Article

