9.7 Statistical tests

For details, see the statistical section under 8.3.

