9.8 Suspension of research

This is pilot study, but after periodic evaluation of study result and safety profile, the PI can terminate the research anytime based on outcomes of periodic safety monitoring and benefit/risk outcomes and will inform the IRB if such a decision is being made.

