15.3 PI Time devoted to conducting the research

The PI will work closely with the study team members and has allocated sufficient time to successfully complete research related procedures, including study enrollment, data collection and data analysis. There will be regular meetings with study investigators to allow ongoing discussions, interim analyses and to address any operational issues.

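### Cumulative outcome data go to team discussion, investigator meetings and the PI with no rule on whether they are pooled or by arm, so nothing protects the blinding in 7.4.5 from interim results

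*Combined protocol and SAP*

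**What the plan says.** The relevant statements are spread over several sections.

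- **What is reviewed (9.2).** Primary outcome and safety data: "Neurological function determined by NIHSS, mRS, MOCA, BI and GOS, discharge disposition and rate of infection will be reviewed". Liver function tests are added.
- **How often, and with whom (9.6).** Periodically, "after collecting data of 5 patients, and will be discussed with team members approximately every three months".
- **Investigator meetings (15.3).** There are to be "regular meetings with study investigators to allow ongoing discussions, interim analyses", as well as discussion of operational matters.
- **Who may stop the study (9.8).** Following periodic evaluation of results and safety, "the PI can terminate the research anytime based on outcomes of periodic safety monitoring and benefit/risk outcomes".
- **Which tests (9.7).** The reader is told to "see the statistical section under 8.3", where the outcome models compare PGZ with placebo.
- **Named reviewers.** Section 9.5 names the independent safety monitor as reviewer of both efficacy and safety. Section 9.1 gives the PHS statistician one look, at half enrolment in each arm, with early stopping in view if the alpha is reached.
- **Blinding (7.4.5).** "The investigators, study staff, subjects, and caregivers will be blinded" to each subject's assignment until the trial ends.
- **Who scores and judges.** Certified study personnel perform BI, GOS and MOCA (7.2.1). The investigator decides whether an adverse event may be drug-related (18.3).

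**The concern.** The issue is who sees interim results and who acts on them. It is not the number of looks or the type I error.

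The plan takes care to protect the blind elsewhere: block sizes are withheld from those who collect and review outcomes (7.4.3), blood samples are coded, and nurses are warned not to disclose capsule contents (7.4.5). It sets no comparable barrier around cumulative results. The people who attend the team and investigator meetings include the people whom 7.4.5 blinds, and the outcome scales depend on a rater.

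If a blinded rater or investigator learns how the arms are diverging, even under coded labels, that knowledge can colour later scoring, attribution of adverse events, withdrawals and the choice of whom to approach. In a study of 50 patients meant to supply the power analysis for a larger trial (8.2), such bias would carry forward into the next design.

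**Working it through.** The plan gives no figure to reproduce here. The check is to set the passages side by side, with short arithmetic on timing.

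**Step 1: does the text state the level of access?** Sections 9.2, 9.6, 9.8 and 15.3 name the data, the timing, the audience and the decision. None says pooled or by arm. No section describes separate open and closed reports or any other firewall.

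**Step 2: do the stated purposes need by-arm data?**

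- Judging the efficacy of PGZ (9.5) needs a comparison with placebo.
- Reaching an alpha early (9.1) needs a test between arms.
- The 8.3 models cited in 9.7 are PGZ-versus-placebo models.
- Benefit in the benefit/risk judgement of 9.8 cannot be read from pooled scores. Serious harm sometimes can be.

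By-arm results will therefore exist during the trial. The documents do not say where they stop.

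**Step 3: who could receive them?** Section 9.6 says team members, 15.3 says study investigators, and 9.8 says the PI. Section 7.4.5 blinds investigators and study staff, so these audiences overlap with the blinded group. Section 7.2.1 makes study personnel the raters of BI, GOS and MOCA at baseline. Sections 7.2.5 and 7.2.6 repeat those scales at discharge and day 90 without naming a different rater.

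**Step 4: how often?** Inputs: "This study will enroll 50 hyperglycemic acute ischemic stroke patients" (8.1), "n=25 per treatment arm, study drug and placebo, respectively" (8.2), and accrual over one year (7.2.1).

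- Team discussion every three months: 50 / 4 = 12.5 patients between discussions, about 4 discussions during accrual.
- Review after 5 patients, if this repeats: 50 / 5 = 10 reviews.
- Safety monitor after every 10th patient (9.1, 19.1.2): 50 / 10 = 5 reviews.
- Statistician once at 50% per arm (9.1): 0.5 × 25 = 12.5 per arm, that is 25 of 50 patients.

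The sections thus give several review schedules and do not say how they relate.

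**Step 5: what follows under each reading?** If the team and PI see by-arm results, the blinding in 7.4.5 is undermined. If they see pooled data only, 7.4.5 is intact, but 9.8 must then mean that the PI relies on someone else's comparative judgement. The independent monitor could supply it, yet no section gives the monitor a route for recommending a pause or stop.

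**The case against.** The strongest reply is that no passage says by-arm results go to the team or the PI. Section 7.4.5 protects each subject's assignment, and pooled summaries at meetings would respect it. The only individual named as reviewing efficacy is independent of the team, and the look tied to the alpha belongs to the statistician. Section 9.7 is only a cross-reference; it does not say that the 8.3 models are run at every review. This all stands, and it limits the point to an unstated access rule.

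Four stronger inferences are tempting, and the documents do not support them.

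- *That 9.6 and 9.8 flatly contradict 7.4.5.* They would conflict only if by-arm data were shared, which is not stated.
- *That the team discusses results every few patients.* The 5-patient figure belongs to the review and need not mean every 5. Discussion is about quarterly.
- *That 9.8 fails whether the data are pooled or by arm.* The PI could act on the monitor's conclusion without seeing by-arm tables.
- *That small by-arm tables would let staff work out individual allocations.* This presumes that such tables are shown to people who know each patient's scores. The text does not say so, and no identification rate should be quoted.

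The reply does not dispose of the gap. Section 15.3 puts interim analyses in investigator meetings, 9.2 puts the outcome scales in the reviewed data, and nothing tells staff who follow these sections to keep by-arm results out of the room.

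**Conclusion.** The point holds as a gap in access control. The plan routes cumulative outcome data to blinded raters, investigators and the PI, needs by-arm results for several stated purposes, and sets no barrier between the two. If by-arm results cross over, the blinding in 7.4.5 is undermined and scoring, causality judgements and enrolment decisions may be biased.

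The bias is a risk conditional on disclosure; its size cannot be derived from the documents. The only figures that apply are those on timing: about 4 team discussions during accrual, assuming even recruitment of 50 patients over one year, and up to 10 reviews if the 5-patient interval repeats. The exploratory aim lowers the stakes for a confirmatory claim. It does not remove the reason for the change, because the outcomes are rater-scored and are meant to inform a later trial.

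**What to change.** Amend 9.5, 9.6, 9.8 and 15.3 as follows:

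1. By-arm cumulative data pass only from the PHS statistician to the independent safety monitor.
2. Team and investigator meetings see only pooled summaries of safety, recruitment and data quality, with no efficacy scales.
3. After each review the monitor sends the PI and the IRB a written recommendation to continue, pause or stop. The PI acts on it under 9.8 without seeing by-arm results.
4. Interim analyses are removed from the purposes of the investigator meetings in 15.3.
5. The review frequencies in 9.1, 9.6 and 19.1.2 are reconciled, stating for each review who receives what.

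This assigns access to data and sets no clinical stopping criterion. The cost is protocol wording, since the statistician and the monitor are already in place. The downside is that the team loses informal sight of efficacy data while the trial runs.
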